#### 4.2.2.2 Logistic regression

Certain binary outcome variables, e.g. response outcomes, will be evaluated using a logistic regression model with treatment regimen, weight, stratum if applicable. Odds ratios will be computed for comparisons of AIN457 regimens versus control(s) utilizing the logistic regression model fitted.

SAS code for logistic regression:

```
Proc logistic data=aaa;  
  Class TRT STRATA / param=glm;  
  Model AVAL = TRT WEIGHT STRATA;  
  Lsmeans TRT / diff cl exp;  
  Ods output diffs=lsm_diff;  
  Run;
```

Logistic regression will be applied to response variables at each visit.

In cases where logistic regression doesn't converge, Fisher's exact test will be applied for comparisons of between AIN457 doses. In this case, no odds ratios or confidence intervals will be estimated, but p-values may be calculated.

```
Proc freq data=aaa;  
  Table TRT * AVAL / fisher;  
  Where TRT in ("AIN457 xx mg" "Placebo");  
  Run;
```

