### **2.5.2 Statistical hypothesis, model, and method of analysis**

The statistical hypothesis for ACR20 being tested is that there is no difference in the proportion of subjects fulfilling the ACR20 criteria at Week 16 in the secukinumab regimens versus placebo regimen.

Let  $p_j$  denote the proportion of ACR20 responders at Week 16 for treatment regimens  $j$ ,  $j=0, 1, 2, 3$  where

- 0 corresponds to placebo regimen,
- 1 corresponds to secukinumab 300 mg,
- 2 corresponds to secukinumab 150 mg,
- 3 corresponds to secukinumab 150 mg no load,

In statistical terms,  $H_0: p_j = p_0$ ,  $H_{A_j}: p_j \neq p_0$ , for the  $j^{\text{th}}$  secukinumab regimen, i.e.

$H_1:$  secukinumab 300 mg is not different to placebo regimen with respect to signs and symptoms (ACR20 response) at Week 16

$H_2:$  secukinumab 150 mg is not different to placebo regimen with respect to signs and symptoms (ACR20 response) at Week 16

$H_3:$  secukinumab 150 mg no load is not different to placebo regimen with respect to signs and symptoms (ACR20 response) at Week 16

The primary endpoint of ACR20 at Week 16 in the FAS will be evaluated using a logistic regression with treatment and randomization stratum (TNF $\alpha$  status -naive or IR) as factors and weight as a covariate. Odds ratios will be computed for comparisons of secukinumab regimens versus placebo regimen utilizing the logistic regression model fitted.

The primary estimand of ACR20 response is the odds-ratio (each secukinumab dose vs. placebo) at week 16 in the FAS population that would be observed if all patients dropping out or being unblinded before week 16 or having with missing ACR20 data at week 16 were non-responders.

The overall testing strategy is explained in [Section 2.6.2.1](#).

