Each of the hypotheses (H1, H2 and H3) for the primary objective (ACR20 at Week 16) for each secukinumab regimen vs. placebo will be tested simultaneously at  $\alpha/3$ . Then based on the rejection of one or more (of H1, H2 and H3), the vdH-mTSS at Week 24 endpoint will be tested hierarchically for each dose (through H4, H5 or H6) at the level of  $\alpha/3$ . If anyone is rejected, then half (1/2) of  $\alpha/3$  will be passed on to each of the other two hypotheses of ACR20 if they were not already rejected.

If  $H_1$  to  $H_6$  in the first family are all rejected, then AIN457 300 mg for all variables in the second family will be tested hierarchically at  $\alpha$  starting from PASI75 ( $H_7$ ). If all variables in AIN457 300 mg group are rejected then test AIN457 150 mg group and finally AIN 457 150 mg No Load group for all variables in hierarchy. Of note, in the description above, rejection of a hypothesis refers to rejection of the two-sided hypothesis; however the level of a rejected hypothesis is only passed on according to the graphical procedure for the test of another hypothesis if the treatment effect is in favor of secukinumab.

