#### **4.2.2 Analysis of binary (and categorical) data**

##### **4.2.2.1 Analyses of Frequencies**

Summary statistics for discrete variables will be presented in contingency tables and will include count and frequency in each category. For n subjects, each at risk to experience a certain event with probability  $\pi$ , the crude incidence is estimated as  $p=x/n$ , where x is the number of subjects with the event.

If applicable, 95% confidence intervals for the relative frequencies will be derived as well based on the score method including continuity correction [Newcombe (1998)]:

With  $z$  as  $(1-\alpha/2)$ -quantile of the standard normal distribution (SAS:  $z=\text{PROBIT}(1-\alpha/2)$ ),  $n$  as total number of subjects (i.e. number of subjects in the denominator), and  $p$  as estimated crude incidence (number of subjects with event /  $n$ ) it is  $q=1-p$

Then the lower limit is

$$L = \max\left(0, \frac{2np + z^2 - 1 - z\sqrt{z^2 + 2 - \frac{1}{n} + 4p(nq+1)}}{2(n+z^2)}\right)$$

and the upper limit is

$$U = \min\left(1, \frac{2np + z^2 + 1 + z\sqrt{z^2 + 2 - \frac{1}{n} + 4p(nq-1)}}{2(n+z^2)}\right).$$

In addition, if  $L > p$  then  $L = p$  and if  $U < p$  then  $U = p$ .

For binary response variables (e.g. for ACR20/50/70, HAQ-DI responder, PASI 75, IGA response) the placebo-adjusted response rates including 95% confidence interval will be derived.

SAS code for risk difference:

```
Proc freq data=acr order=formatted;
```

```
Tables response*trt/ riskdiff;
```

```
Run;
```

(Note the response value should be sorted with '1' ahead of '0'.)

Fisher's exact test will be applied to rare events (e.g., MCR), pairwise treatment group comparisons to placebo or active controls.

SAS code for Fisher's exact test:

```
Proc freq data=mcr order=formatted;
```

```
Tables response*trt/Fisher;
```

```
Run;
```

If appropriate, an exact  $100*(1-\alpha)\%$  confidence interval (Clopper-Pearson 1934) will be obtained by using the SAS procedure PROC FREQ with the EXACT BINOMIAL statement. However, the confidence interval derived via the score method including continuity correction will be the default in safety analyses.

Figures will be provided for primary and secondary variables, with means and 95% confidence intervals displayed across time for all the treatment groups.

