  rupp = 1/(1+exp(-uclmean));  
run;
```

Of note, sometimes all responses may be imputed to 0 or 1 at a given combination of response variable, treatment group and visit. Such cases should be considered separately. The combined final response rate would be the same as the original response but the 95% CI will be undefined.

The odds ratio will be derived using GENMOD for each imputation, then combined using Rubin's rules again.

```
proc genmod data = acr20_mi descending;  
  by avisitn _imputation_;  
  class trt_ TNFRESN ;  
  model aval = trt_ TNFRESN weight / link=logit dist=bin;  
  lsmeans trt_ / diff;  
  estimate 'AIN457 150 mg vs No Load' trt_ 1 -1 0 0;  
  estimate 'AIN457 150 mg vs Placebo' trt_ 1 0 0 -1;  
  estimate 'AIN457 150 mg No Load vs Placebo' trt_ 0 1 0 -1;  
  estimate 'AIN457 300 mg vs Placebo' trt_ 0 0 1 -1;
```

```
ods output Estimates=imp_est;
run;
proc mianalyze data=imp_est;
  by avisitn trt_;
  modeleffects LBetaEstimate;
  stderr StdErr;
  ods output ParameterEstimates=_res;
run;
```

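### The PROC LOGISTIC code in SAP 4.2.2.2 names no event level; if AVAL is 0/1 with 1 = response, it reports the reciprocal of the stated odds ratio

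*SAP*

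**What the plan says.** SAP 2.5.2 specifies the primary model: "The primary endpoint of ACR20 at Week 16 in the FAS will be evaluated using a logistic regression with treatment and randomization stratum", with weight as a covariate. It defines the target quantity: "The primary estimand of ACR20 response is the odds-ratio (each secukinumab dose vs. placebo) at week 16 in the FAS population", with dropouts, unblinded patients and missing data counted as non-responders. SAP 2.6.2.2 uses the same form of model for ACR50, PASI75, PASI90 and the presence of enthesitis and dactylitis.

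The implementing code is in SAP 4.2.2.2. It opens with "Proc logistic data=aaa", fits "Model AVAL = TRT WEIGHT STRATA", and takes the odds ratios from "Lsmeans TRT / diff cl exp". No statement carries an event, reference, descending or order option, and no note describes the coding of AVAL. The section applies the model at each visit.

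Three other code blocks in the same appendix do address the response level:

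- In 4.2.2.1 the PROC FREQ risk-difference code carries the remark "Note the response value should be sorted with '1' ahead of '0".
- In 4.2.3 the multiple-imputation response rate uses `level=2`, the second ordered value.
- In 4.2.3 the multiple-imputation odds ratio begins "proc genmod data = acr20_mi descending", and its response variable is also called aval.

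**The concern.** PROC LOGISTIC models the first ordered response value unless told otherwise. With ascending 0/1 data that value is 0. If 1 means response, the printed code estimates the odds of non-response, and the exponentiated treatment differences are reciprocals of the odds ratios that SAP 2.5.2 and 2.6.2.2 define.

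What is at stake is the reported effect measure for the primary endpoint and several secondary endpoints. The odds ratio and its confidence limits would not be those of the stated estimand. They would also sit on the inverse scale to the multiple-imputation odds ratios in 4.2.3, where the event level is reversed explicitly, so a reader comparing the two tables would see apparent disagreement in direction.

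**Working it through.** **The plan's own figure.** SAP 3 gives over 99% power for ACR20 at 51% versus 15%, 220 versus 330 subjects, two-sided 1.67%, Fisher's exact test. Exact enumeration gives power above 0.9999, so the figure reproduces. It does not depend on which level is modelled.

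**Which coding the SAP implies.**

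| SAP code | Event handling | Implication |
|---|---|---|
| 4.2.3, response rate | `level=2` | response sorts second |
| 4.2.3, GENMOD on aval | `descending` | response has the higher value; order reversed to model it |
| 4.2.2.1, PROC FREQ | note to put 1 first | values are 1 and 0; some step must reorder them |
| 4.2.2.2, PROC LOGISTIC | none | first ordered value is modelled |

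The two entries from 4.2.3 fit ascending 0/1 with 1 = response. The 4.2.2.1 entry confirms the values, but not their order in the data set that PROC LOGISTIC reads.

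**Treatment order does not cancel the effect.** If TRT carries labels like those in the SAP's code (AIN457 with a dose, and Placebo), AIN457 sorts before Placebo and the differences are AIN457 minus placebo. Only the modelled level inverts the ratio.

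**Algebra.** logit(1 − p) = −logit(p). Modelling 0 instead of 1 changes the sign of every coefficient. The odds ratio becomes 1/OR, and the confidence limits become the reciprocals of the opposite limits. The Wald statistic keeps its absolute value, so the two-sided p-value is the same.

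**Size at the planning rates in SAP 3.** OR = [p1/(1 − p1)] / [p0/(1 − p0)], with p1 for secukinumab and p0 for placebo. For ACR20: (0.51/0.49)/(0.15/0.85) = 1.0408/0.1765 = 5.90; reciprocal 0.170.

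| Endpoint | p1 | p0 | OR, event = 1 | OR, event = 0 |
|---|---|---|---|---|
| ACR20 | 0.51 | 0.15 | 5.90 | 0.170 |
| ACR50 | 0.35 | 0.07 | 7.15 | 0.140 |
| PASI75 | 0.48 | 0.16 | 4.85 | 0.206 |
| PASI90 | 0.33 | 0.09 | 4.98 | 0.201 |
| Enthesitis present* | 0.58 | 0.79 | 0.367 | 2.72 |
| Dactylitis present* | 0.50 | 0.85 | 0.176 | 5.67 |

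*If presence is coded 1. If resolution is coded 1, the two columns swap.

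**Check on fitted models.** One simulated trial (220/220/220/330, the ACR20 planning rates, with an assumed weight distribution and a 30% TNF-IR stratum) was fitted both ways. With event = 1 the three odds ratios were 5.06, 6.30 and 5.07. With event = 0 they were 0.198, 0.159 and 0.197. For the first comparison the 95% limits were 3.40 to 7.53 and 0.133 to 0.294, and the p-value was 1.4 × 10⁻¹⁵ in both fits. SAS was not available, so the default event level is taken as standard behaviour of the procedure and was not run.

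**The case against.** The strongest reply is that the SAP never states how AVAL is coded or formatted in the data set that PROC LOGISTIC reads. The evidence for 0/1 comes from other data sets. The remark in 4.2.2.1 can be turned round: it sits under formatted ordering, where plain 0/1 puts 0 first, so obeying it needs a format or recoding that sorts response first. If AVAL were prepared that way for PROC LOGISTIC too, the printed code would be correct. The block is also a template with dummy names, and a programmer would work to the estimand in 2.5.2. All of this stands, and it is why the point is conditional. It does not remove the omission, because the two blocks in 4.2.3 point the other way and nothing in 4.2.2.2 settles it.

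A reader might infer two further consequences that the documents do not support.

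- **Alpha passing.** SAP 2.6.2.1 passes a level on only "if the treatment effect is in favor of secukinumab". It does not say that direction is read from the PROC LOGISTIC output. SAP 4.2.2.1 separately plans placebo-adjusted response rates with confidence intervals. An odds ratio of 0.17 beside 51% versus 15% would be recognised as inverted. No wrong testing decision is shown.
- **Conflict on one estimand.** The primary analysis counts dropouts and missing data as non-response, whereas 4.2.3 imputes under missing at random. They are different estimands, and the issue between them is only the reporting scale.

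**Conclusion.** The point holds in conditional form. The code for the primary logistic model leaves the event level open. On the coding that SAP 4.2.3 indicates, running it as printed reports 1/OR: about 0.17 instead of 5.90 for ACR20, with similar inversions for ACR50, PASI75 and PASI90. For enthesitis and dactylitis no inversion can be established. SAP 2.6.2.2 models presence but describes missing subjects as non-responders, so whether benefit appears as an odds ratio above or below 1 is undefined until the coding is stated.

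The damage is confined to the reported odds ratios, their confidence limits and their agreement in scale with the multiple-imputation results. The conclusion rests on two assumptions: that AVAL is 0/1 with 1 = response in the analysis data set, and that the software default is the first ordered value.

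**What to change.** In SAP 4.2.2.2, write the statement as `Model AVAL(event='1') = TRT WEIGHT STRATA;` and add that AVAL = 1 means response. For enthesitis and dactylitis, state whether 1 means presence or resolution, and match the missing-data rule in 2.6.2.2 to that choice.

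This costs one option and a sentence or two. Hypotheses, model terms, sample size and data collection are untouched.

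### The SAP's fallback for a failed logistic model contradicts its own code, ignores separation and yields no odds ratio, which affects supportive by-visit and TNF-subgroup results but not the Week 16 tests

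*SAP*

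**What the plan says.** SAP 4.2.2.2 sets out the logistic model for binary outcomes. Its code adjusts for weight and stratum ("Model AVAL = TRT WEIGHT STRATA"), odds ratios against control are promised, and the scope is wide: "Logistic regression will be applied to response variables at each visit".

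The fallback follows: "In cases where logistic regression doesn't converge, Fisher's exact test will be applied for comparisons of between AIN457 doses". On output it adds: "In this case, no odds ratios or confidence intervals will be estimated, but p-values may be calculated". The code printed directly below requests a plain two-way table, "Table TRT * AVAL / fisher", and restricts the data to one secukinumab dose and placebo.

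For the primary endpoint, SAP 2.5.2 says: "The primary estimand of ACR20 response is the odds-ratio (each secukinumab dose vs. placebo) at week 16 in the FAS population". SAP 2.6.2.2 defines odds-ratio estimands in the same way for ACR50, PASI75, PASI90, dactylitis and enthesitis, all at Week 16. SAP 2.2.1 adds that primary and secondary endpoints will be evaluated by TNF-alpha inhibitor status, without naming an effect measure.

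**The concern.** Three features of the rule do not fit together.

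- **Scope.** The prose covers dose against dose and the code covers dose against placebo. Read literally, the prose leaves placebo comparisons without a fallback, and the code leaves dose comparisons without one.
- **Trigger.** The usual cause of trouble is a treatment group with no responders. The likelihood then flattens while one coefficient drifts towards infinity. Software may or may not call that non-convergence. If it does not, a meaningless odds ratio can be tabulated and the fallback is never invoked.
- **Output.** When it is invoked, the adjustment for weight and TNF stratum disappears, and so do the odds ratio and its interval.

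At stake are the supportive odds ratios at early visits, for high-threshold endpoints and within the TNF-IR subgroup, where placebo responses may be sparse. If the rule stays unclear, the choice of method is made after the data have been seen.

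**Working it through.** **1. The plan's own figure.** SAP section 3 gives power over 99% for PASI90, the sparsest powered endpoint in the psoriasis subset: 9% against 33%, 165 against 110 subjects, Fisher's exact test, two-sided 1.67%. Exact enumeration gives 99.47%, so the figure reproduces.

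**2. Empty placebo cell at Week 16.** The chance of no responders among n subjects with response rate p is (1 − p)^n. With the rates and group sizes of SAP section 3:

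| Endpoint | n | p | (1 − p)^n |
|---|---|---|---|
| ACR20 | 330 | 15% | 5e-24 |
| ACR50 | 330 | 7% | 4e-11 |
| PASI75 | 165 | 16% | 3e-13 |
| PASI90 | 165 | 9% | 2e-7 |

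**3. TNF-IR subgroup at Week 16.** Protocol 3.1 and 5.3 target 30% TNF-IR. That gives 330 × 0.3 = 99 placebo subjects, and 165 × 0.3 ≈ 50 in the psoriasis subset. Assuming the planning rates also hold in this subgroup:

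- ACR20: 0.85^99 = 1e-7
- ACR50: 0.93^99 = 0.08%
- PASI75: 0.84^50 = 0.02%
- PASI90: 0.91^50 = 0.9%

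**4. Early visits.** The documents give no placebo rates here, so the range below is assumed:

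| Assumed placebo rate | n = 165 | n = 50 |
|---|---|---|
| 0.5% | 44% | 78% |
| 1% | 19% | 61% |
| 2% | 3.6% | 36% |
| 3% | 0.7% | 22% |

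**5. Which contrast fails, and whether the trigger notices.** A four-arm maximum-likelihood fit with treatment, weight and stratum used invented counts: 5, 8 and 12 responders of 110 in the active arms and 0 of 165 on placebo. Weight and stratum were simulated.

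- The dose contrasts were stable. The log odds ratio for 12/110 against 5/110 was 0.906 (SE 0.55), an odds ratio of exp(0.906) = 2.47.
- The placebo coefficient ran from −6.5 at iteration 8 to −13.5 at 15 and −22.5 at 25, with a final SE of about 16,700. The deviance settled at 172.42.
- The software declared convergence by iteration 25. It was Python, not SAS, so this shows only that a convergence flag need not detect separation.

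The prose therefore covers the contrast that survives and omits the one that fails.

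**6. Whether an estimate can still be given.** For a single two-by-two table, the Firth odds ratio equals the one obtained by adding 0.5 to each cell. Counts are invented and unadjusted:

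- 10/110 against 0/165: (10.5 × 165.5)/(100.5 × 0.5) = 34.6, Wald 95% CI 2.0 to 597; Fisher p = 0.00008; exact conditional lower limit 3.58.
- 5/110 against 0/165: (5.5 × 165.5)/(105.5 × 0.5) = 17.3, Wald 95% CI 0.94 to 315; Fisher p = 0.0097; exact conditional lower limit 1.40.

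In the second table the Wald interval includes 1 although Fisher's p is below 0.01. Wald intervals are unreliable in such tables, hence the preference for profile-likelihood intervals below.

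**The case against.** The strongest reply is that nothing confirmatory depends on this rule. A reader might infer that sparse visits and subgroups lose the stated estimand. The documents do not support that. For these response endpoints the odds-ratio estimands are stated for Week 16 in the FAS or its baseline subsets, and none is stated for other visits or for TNF subgroups. The testing strategy in SAP 2.6.2.1 contains no early-visit or subgroup hypothesis. This objection stands in full.

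The SAP also partly covers the gap. SAP 4.2.2.1 provides a placebo-adjusted response rate with 95% CI for binary responses, so an effect measure survives, although unadjusted. The same section applies Fisher's test to rare events against placebo or active controls. That suggests the code in 4.2.2.2 shows the intent and the sentence is garbled. It is a separate rule, however, and does not correct the sentence. SAP 4.2.3 foresees imputed responses that are all 0 or all 1 and says how to report the response rate, but gives no rule for the odds ratio.

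It is also fair to say that Fisher's test is valid in a sparse table, that a penalised interval such as 2.0 to 597 conveys little beyond direction, and that the larger zero-cell probabilities rest on assumed rates. All of this limits the importance of the point. None of it resolves the conflict between prose and code or supplies the missing trigger.

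SAP 2.5.4 and parts of 2.7 are not in the public text, so further rules there cannot be excluded.

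**Conclusion.** The point holds as a minor one. The fallback contradicts its own code, does not name separation, and discards both the adjustment and the odds ratio. The consequence is confined to supportive by-visit and TNF-subgroup odds ratios with sparse placebo response. The Week 16 primary and secondary binary tests and their stated estimands are unaffected, given the planning rates in SAP section 3.

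How often the rule would matter cannot be determined from the documents. At the planning rates, and assuming they hold in TNF-IR subjects, it would matter less than 1% of the time per endpoint. At early visits the probability depends entirely on the assumed placebo rate.

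**What to change.** In SAP 4.2.2.2:

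1. Reword the fallback to cover secukinumab against placebo and comparisons between secukinumab doses, and align the code with it.
2. Trigger it on non-convergence or on any report of complete or quasi-complete separation.
3. Use Firth penalised logistic regression with treatment, weight and TNF stratum, omitting the stratum within TNF subgroups where it is constant. Report the odds ratio with a profile-likelihood CI. Fisher's p-value can stay as supportive information.

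The cost is a few sentences and one model option. Intervals will be wide where cells are sparse. Exact stratified logistic regression would be a reasonable alternative; what matters is that one adjusted method giving an estimate and interval is named in advance.

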#### 4.2.2.3 Cochran-Mantel-Haenszel Test

The CMH test will be performed using the SAS procedure PROC FREQ with the CMH option.

#### 4.2.3 Multiple Imputation

A multiple imputation will be performed based on MAR by treatment group for baseline weight, baseline and post-baseline of each parameter for visits up to the primary time point (e.g Week 16 or 24) using Markov Chain Monte Carlo (MCMC) method with EM algorithm.

Impute the missing values 100 times (NIMPUTE) with a seed=457<studycode> as shown below:

```
proc mi data= out=imp minmaxiter=10000000 nimpute=100 seed=4572342;  
  by trt;  
  var weight_base strata var1_base var1_week1-var1_week24;  
  mcmc chain=multiple initial=em;  
  run;
```

If needed repeat for each component necessary to calculate the final score, e.g. as follows:

```
proc mi data=imp out=imp2 minmaxiter=10000000 nimpute=100 seed=4572342;  
  by trt _imputation_ ;  
  var weight_base strata var2_base var2_week1-var2_week24;  
  mcmc chain=multiple initial=em;  
run;
```

Post-processing of out of range imputed values will be processed with the min and max values of each variable.

The score and ACR response can now be calculated based on the complete data. The response rate will be calculated for each imputation and then combined using Rubin's rules.

In order to calculate the response rate for each imputation, PROC FREQ will be used as follows. Calculate binomial proportion and standard error for each imputation.

```
proc freq data=<ACR20>;  
  by treat visit _imputation_ ;  
  tables <response> / binomial (level=2 cl=wilson correct) ;  
  ods output BinomialProp=imp_bpr;  
run;
```

Transpose the dataset for subsequent use with PROC MIANALYZE.

```
proc transpose data=imp_bpr out=imp_trs(drop=_name_) ;  
  by treat visit _imputation_ ;  
  var nvalue1; id name1; idlabel labell;  
run;
```

Apply LOGIT transformation:  $y=\log(p/(1-p))$  and std. err. transformation: <new se> =  $se/(p*(1-p))$

```
data logit;  
  set imp_trs(rename=(_bin_=p e_bin=se));  
  by treat visit _imputation_ ;  
  lmean=log(p/(1-p));  
  lse=se/(p*(1-p));  
run;
```

The transformed binomial proportion estimates and standard errors are combined by applying Rubin's rules for multiple imputed data sets.

```
proc mianalyze data=logit;  
  by treat visit ;  
  modeleffects lmean;  
  stderr lse;  
  ods output ParameterEstimates=logitres;  
run;
```

The combined data should be transformed back using the following formula:  $p=1/(1+\exp(-y))$

```
data miexpress;  
  set logitres;  
  by treat visit ;  
  resti = 1/(1+exp(-estimate));  
  rlow = 1/(1+exp(-lclmean));  
  rupp = 1/(1+exp(-uclmean));  
run;
```

Of note, sometimes all responses may be imputed to 0 or 1 at a given combination of response variable, treatment group and visit. Such cases should be considered separately. The combined final response rate would be the same as the original response but the 95% CI will be undefined.

The odds ratio will be derived using GENMOD for each imputation, then combined using Rubin's rules again.

```
proc genmod data = acr20_mi descending;  
  by avisitn _imputation_;  
  class trt_ TNFRESN ;  
  model aval = trt_ TNFRESN weight / link=logit dist=bin;  
  lsmeans trt_ / diff;  
  estimate 'AIN457 150 mg vs No Load' trt_ 1 -1 0 0;  
  estimate 'AIN457 150 mg vs Placebo' trt_ 1 0 0 -1;  
  estimate 'AIN457 150 mg No Load vs Placebo' trt_ 0 1 0 -1;  
  estimate 'AIN457 300 mg vs Placebo' trt_ 0 0 1 -1;
```

```
ods output Estimates=imp_est;
run;
proc mianalyze data=imp_est;
  by avisitn trt_;
  modeleffects LBetaEstimate;
  stderr StdErr;
  ods output ParameterEstimates=_res;
run;
```

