## **Rescued patients**

[figure not shown]
In general if not stated otherwise (as e.g. for vdH-mTSS), the handling of data for subjects who are **rescued at Week 16** will be handled in the following fashion for comparison with placebo at Week 20 and Week 24:

[figure not shown]
For each binary endpoint, a subject will be considered as a non-responder at Week 20/24 for that endpoint if the subject is a non-responder (including missing imputed non-responder) at Week 16. If a subject is a responder at Week 16 for that endpoint, the actual value at Week 20/24 will be used (missing is considered as non-responder). This will be done for all treatment regimens in order to minimize bias.

[figure not shown]
- For continuous endpoints, the goal of the analyses would be to estimate what would have happened if the patients had stayed on the original treatment. Thus, the data collected after a Placebo patient switches to secukinumab will be treated as missing for the placebo group and will be analyzed using a mixed-effects repeated measures model (MMRM) which is valid under the missing at random (MAR) assumption. For secukinumab patients that are rescued, the actual values will be used in the analysis.

[figure not shown]
Data collected **after Week 24** will generally be presented as ‘observed case’; i.e. all available data for each time point will be included in the analyses. In addition, multiple imputation will be used for long-term (e.g. after week 52) comparison for selected endpoints.

For comparisons between the active arms the rescue penalty will not be applied as the effect of rescuing is the same for both treatment groups (i.e. the patient continues to receive secukinumab 150 mg or 300 mg every 4 weeks).

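### The sample multiple-imputation code for a second component imputes 100 times within each of 100 existing imputations, with the same seed and without the other components, so MI-based ACR standard errors are too small if it is followed

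*SAP*

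**What the plan says.** SAP section 4.2.3 sets the number of imputations in prose: "Impute the missing values 100 times (NIMPUTE) with a seed=457<studycode> as shown below". The first sample call does this for one variable: "proc mi data= out=imp minmaxiter=10000000 nimpute=100 seed=4572342".

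For scores built from several parts the SAP adds "If needed repeat for each component necessary to calculate the final score, e.g. as follows". The second call is "proc mi data=imp out=imp2 minmaxiter=10000000 nimpute=100 seed=4572342". It takes the output of the first call as input, processes it "by trt _imputation" (so within each existing imputation), and its model is "var weight_base strata var2_base var2_week1-var2_week24": weight, stratum and the second component's own baseline and visits.

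The section then says that the ACR response is derived from the completed data. PROC FREQ and GENMOD run once per imputation index, and MIANALYZE combines the results by ordinary Rubin's rules. No step creates a combined index or applies rules for nested imputations.

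SAP 2.12.4.1 defines ACR20 from seven components: tender and swollen joint counts, plus at least three of five other measures. For the primary analysis, SAP 2.5.2 and 2.5.3 count subjects with missing ACR20 as non-responders.

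**The concern.** There are three separate faults in the sample code.

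- **Nesting.** The second call multiplies the number of completed data sets by 100, which contradicts the stated 100. The pooling steps have no means of handling the extra layer. What suffers is the variance: standard errors and confidence intervals for MI-based response rates and odds ratios.
- **Separate models.** ACR20 needs several components to improve together. Imputing each from its own history alone drops the remaining correlation between components in the imputed records, so the imputed response rate can be wrong.
- **One seed.** The same seed is fixed in both calls. If the random streams line up, artificial correlation between components could result.

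MI results are usually read as a check on non-responder imputation. Confidence intervals that are falsely narrow, or shifted rates, would undermine that check.

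**Working it through.** The code was read, not executed.

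**1. Number of imputations.** Stated: 100. With one component the code gives 100 records per subject, or 990 × 100 = 99,000 rows, which matches. With two components it gives 100 × 100 = 10,000 per subject, or 990 × 10,000 = 9.9 million rows, which does not match. If later calls used `nimpute=1`, the count would stay at 100.

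**2. Within-imputation standard error.** Inputs are the SAP section 3 planning rates and group sizes. Formula: SE = √(p(1 − p)/n). If 100 copies of each subject share one index value, n becomes 100n and the SE falls by √100 = 10.

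| Group | p | n | Correct SE | SE with 100 copies |
|---|---|---|---|---|
| Placebo | 0.15 | 330 | 0.0197 | 0.0020 |
| Secukinumab | 0.51 | 220 | 0.0337 | 0.0034 |

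This holds whichever index survives: 10,000 records over 100 index values is 100 per subject per value.

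**3. Pooled standard error.** Scale the correct total variance to 1 and let g be the fraction of missing information, so the within part is 1 − g and the between part is g. Dividing only the within part by 100 gives (1 − g)/100 + g.

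- g = 0.05: 0.0095 + 0.05 = 0.0595; √(1/0.0595) = 4.1 times too small.
- g = 0.25: 0.0075 + 0.25 = 0.2575; √(1/0.2575) = 2.0 times too small.

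The values of g are assumptions. The between part is taken as unchanged; averaging over nested draws could shrink it and make the understatement worse. Duplication enters the GENMOD odds ratios in the same way.

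**4. Separate versus joint imputation.** The simulation used seven latent normal components and 400,000 draws per setting, calibrated to ACR20 of 51% and 15%. Two inputs are assumed, because the documents do not give them: correlation between components (0.3, 0.5, 0.7) and correlation of each component with its own history (0.5, 0.7). ACR20 among imputed subjects:

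| Between / own history | Active, separate | Placebo, separate |
|---|---|---|
| 0.3 / 0.5 | 47.2% | 8.7% |
| 0.3 / 0.7 | 48.5% | 10.9% |
| 0.5 / 0.5 | 43.5% | 6.2% |
| 0.5 / 0.7 | 45.8% | 8.9% |
| 0.7 / 0.5 | 38.8% | 4.1% |
| 0.7 / 0.7 | 42.4% | 7.2% |

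Joint imputation returned 50.9–51.2% and 14.9–15.1%.

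The effect of separate imputation on a whole arm is the missing share times the shift. No Week 16 missing share is given. The 25% row borrows the protocol's anticipated first-year dropout (section 4) as an upper value; equal shares in both arms are assumed.

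| Missing share | Arm rate (points) | Active − placebo (points) |
|---|---|---|
| 5% | −0.1 to −0.6 | −0.1 to +0.1 |
| 10% | −0.2 to −1.2 | −0.2 to +0.3 |
| 25% | −0.6 to −3.1 | −0.4 to +0.7 |

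**5. Repeated seed.** In the extreme case where all components share the same noise, imputed ACR20 rose instead, to 56–63% on active and 19–30% on placebo. Whether streams align depends on the software.

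**The case against.** The strongest reply is that this is template code. It is introduced conditionally and by way of example, the input data set of the first call is blank, and the variables are named var1 and var2. The prose states 100 imputations and the pooling method, so the intention is clear. A programmer who found 100 times the expected rows would probably notice.

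This limits how certain the harm is, but it does not remove the defect. ACR is exactly the kind of score for which the repeat is needed, the next text derives the ACR response from these data, and nothing else in the available SAP gives a correct version. Following the code spoils the variance; departing from it is an unplanned choice.

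Four stronger readings should be resisted.

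- *The code cannot run.* For the two calls shown, 9.9 million rows is no size barrier. Chaining all seven components would give 100^7 = 10^14 records per subject, but the SAP does not show that program.
- *It understates ACR response.* Nesting alone does not bias the point estimate. Separate models lowered both arms in the simulation, but shared noise raised them, so the net direction is not fixed.
- *It distorts the long-term comparisons.* SAP 2.6.3 says "multiple imputation will be used for long-term (e.g. after week 52) comparison for selected endpoints", but the code covers visits only up to Week 16 or 24, and nothing says that it will be reused later.
- *It threatens the confirmatory results.* The main analyses of the primary and secondary endpoints use non-responder imputation, MMRM or linear extrapolation.

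The text of SAP 2.5.4 (supportive analyses) is not available, so how widely MI is used for ACR cannot be established. For an endpoint imputed as a single variable, the first call is enough and the nesting does not arise.

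**Conclusion.** The point holds as a defect in the sample code for supportive MI analyses up to Week 16/24. The 10,000 records against a stated 100 follow directly from the text. The 10-fold within-imputation and roughly 2- to 4-fold pooled understatement of the standard error are conditional on the nested copies sharing one index. The pooled figure also rests on the assumed 5–25% missing information and an unchanged between-imputation variance.

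The separate component models can bias MI-based ACR rates, by at most about 3 points per arm over the values tried and by less than 1 point in the treatment difference. These sizes rest on assumed correlations and missing shares. The primary ACR20 analysis is unaffected.

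**What to change.** Replace the sequential example with one PROC MI call per treatment group that holds all ACR components, with `nimpute=100`, and derive ACR response from those 100 completed data sets. The existing pooling steps then apply as written.

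If the joint model is too large to fit stably, keep sequential calls but set `nimpute=1` by treatment group and imputation index in every call after the first, use a different seed in each call, and add the previously imputed components to the variable list.

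The cost is a code edit and a larger imputation model with a longer run time. Protocol Table 6-1 schedules the components at baseline and nine visits to Week 24, so the joint model has about 7 × 10 + 2 = 72 variables in arms of 220 or 330. Stability should therefore be checked before the joint version is fixed in the SAP.
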